3.2. Study Schema

[figure not shown]

3.3. Phase 1b Safety/DLT Assessment

Phase 1b will be conducted with up to 27 subjects enrolled depending on the occurrence of DLTs. The starting dose will be 420 mg and a modified 3+3+3 design will be used (see [Section 5.2.1](#) and Section 3.3.1) to assess DLTs. If DLTs are unacceptably high then the dose of ibrutinib may be reduced sequentially to 280 mg or 140 mg. After completion of Phase 1b, further enrollment into Phase 2 will commence after the RP2D is identified and the initial safety and efficacy data are evaluated as favorable by the Sponsor. Subjects who have not experienced a DLT in Phase 1b (after 4 weeks of ibrutinib treatment) may continue into Phase 2 without interruption at their initial Phase 1b dose.

The decision to proceed with a RP2D or to dose reduce will be made in a Dose Level Review Meeting by the Sponsor in conjunction representative investigators after careful consideration of all available safety and laboratory information.

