Statistical Methods and Data Analysis:	
Phase 1:
 
Designed to determine the RP2D and toxicity profile of ibrutinib using the modified 3+3+3 design. Up to 3 dose levels will be explored. In observing ≤ 2 DLTs in 9 subjects, RP2D is determined.
 
The Phase 1b efficacy data for subjects with RP2D will be combined with Phase 2 efficacy data.
 
Phase 2
 
Primary Efficacy Analysis:
 
Best overall cGVHD response rate is defined as the proportion of subjects who achieve a NIH-defined complete response (CR) or partial response (PR) during the study over all subjects who got RP2D from either Phase 1b portion or Phase 2 portion. The cGVHD response rate along with its 95% exact binomial confidence interval will be presented.
 
Secondary Efficacy Analyses:
 
Secondary efficacy variables including sustained response rate, DOR,

	
corticosteroid requirement changes over time, and change in symptom burden as measured by the Lee cGVHD Symptom Scale will be analyzed descriptively.
 
Efficacy analyses will be performed on all subjects who are enrolled for RP2D from either Phase 1b portion or Phase 2 portion.
 
Safety Analysis:
 
All subjects are to be monitored for adverse events during the study. Other safety measurements include clinical laboratory tests and vital signs. Descriptive statistics will be use to summarize safety data (adverse events [AEs], clinical laboratory tests and vital signs) for all subjects receiving ibrutinib. Summary statistics will include means, standard deviations, and medians for continuous variables and proportions for categorical variables.

Interim Analysis	Not applicable.

ABBREVIATIONS

AE	adverse event
aGVHD	acute GVHD
Allo-HCT	allogenic hematopoietic cell transplant
ALT	alanine aminotransferase
ANC	absolute neutrophil count
ASBMT	American Society for Blood and Marrow Transplantation
ASCO	American Society of Clinical Oncology
AST	aspartate aminotransferase
AUC	area under the curve
BAFF	B cell activating factor
BCR	B-cell receptor
BSA	body surface area
Btk	Bruton's tyrosine kinase
CFR	US Code of Federal Regulations
cGVHD	chronic GVHD
CLL	chronic lymphocytic leukemia
CNS	central nervous system
CRF	case report form
CR	complete response
CTCAE v. 4.03	Common Terminology Criteria for Adverse Events version 4.03
CYP	cytochrome P450
DLT	dose limiting toxicity
DOR	Duration of response
ECG	Electrocardiogram
ECP	extracorporeal photopheresis

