5.2.2. Definition of Dose Limiting Toxicities

The following DLT criteria apply only to Phase 1b of the study. After completing the DLT period (28 days), Phase 1b subjects will be evaluated by standard safety reporting.

A DLT is defined as any drug-related hematologic or non-hematologic toxicity Grade 3 or higher, with the following exceptions:

- Grade 4 nausea, vomiting, or diarrhea or Grade 3 diarrhea defined by ≥ 7 stools/day persisting for greater than 3 days despite best supportive care
- Grade 4 neutropenia or Grade 3 neutropenia persisting for greater than 14 days or Grade 3 neutropenia of any duration with fever
- For subjects with Grade 2 rash at entry, DLT will be progression to Grade 3 AND a doubling of % BSA involvement
- For subjects with Grade 3 rash at entry, DLT will be progression to Grade 4 OR a doubling of % BSA involvement

5.2.3. Phase 2

Following the establishment of the RP2D, the Phase 2 portion of the study will begin accruing additional subjects. Approximately 40 subjects (cumulative from both Phase 1b and Phase 2) will be treated with the RP2D. Subjects enrolled in the Phase 2 part of the study will have met the same inclusion/exclusion criteria as Phase 1b subjects and will be treated with the RP2D. Subjects continuing from Phase 1b and subjects enrolled in Phase 2 will continue to be treated unless they have intervening unacceptable toxicity or meet other criteria for subject discontinuation (see [Section 9](#)).

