10.3. Sample Size Determination

With a sample size of 40 subjects and assuming an best overall cGVHD response rate of approximately 50%, it is expected to have at least 90% power to show the efficacious treatment effect (the lower bound of 95% CI of the response rate >0.25).

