1.4 Sample Size Justification

The Phase 1b part of the study is a modified 3+3+3 dose-finding design that is described in the protocol.

With a sample size of 40 subjects receiving the RP2D, and assuming an overall cGVHD response rate of 50%, the study is expected to have at least 90% power to show the efficacious treatment effect (the lower bound of 95% confidence interval [CI] of the response rate >25%).

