5.1 Primary Endpoint

The primary efficacy endpoint is the best overall cGVHD response rate during the study based on investigator assessments. To assess the primary endpoint, the study used the 2005 NIH Consensus Panel Response criteria with two modifications based on the updated 2014 NIH Consensus Panel Response criteria: 1) “Not Evaluable” can be used for assessments where there is another non-cGVHD cause for the abnormalities documented and 2) a change in cGVHD organ score from 0 to 1 is no longer considered progression as is the case per the 2005 NIH cGVHD Response Criteria.

Best overall cGVHD response rate is defined as the proportion of subjects who achieve a NIH-defined complete response or partial response. The response rate and its 95% confidence interval (CI) will be calculated based on the exact test for binomial distribution. If the lower bound of the CI of the response rate is $\geq 25\%$, the primary efficacy objective is achieved.

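### Protocol 3.3 makes Phase 2 depend on undefined favourable Phase 1b efficacy, and the same subjects are pooled into the primary exact analysis: given that Phase 2 opens the pooled rate is biased upward, and the stated power omits the condition

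*Protocol*

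**What the plan says.** Protocol 3.3 allows Phase 2 enrolment to "commence after the RP2D is identified and the initial safety and efficacy data are evaluated as favorable by the Sponsor". It does not say which efficacy measure is meant, when it is read, or what counts as favourable.

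Other places describe the transition without an efficacy condition. Protocol 5.2.3 says: "Following the establishment of the RP2D, the Phase 2 portion of the study will begin accruing additional subjects". Protocol 3.1 and SAP 1.2 also tie the start of Phase 2 to determination of the RP2D. The synopsis enters interim analysis as not applicable.

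The Phase 1b subjects count in the primary result. The synopsis states: "The Phase 1b efficacy data for subjects with RP2D will be combined with Phase 2 efficacy data". SAP section 5 also combines the two parts. For the primary endpoint, SAP 5.1 says: "The response rate and its 95% confidence interval (CI) will be calculated based on the exact test for binomial distribution". Success is read against 25%.

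Protocol 10.3 assumes 40 subjects and a response rate near 50%, sets the target as "the lower bound of 95% CI of the response rate >0.25", and concludes that "it is expected to have at least 90% power to show the efficacious treatment effect". SAP 1.4 repeats the claim. Neither mentions the condition in 3.3.

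**The concern.** An exact binomial interval on 40 subjects assumes that every subject entered the count regardless of outcome. If Phase 2 opens only when the first 6 to 9 subjects look good, then in any trial that reaches the primary analysis those subjects' responses have been conditioned on. The pooled count is no longer Binomial(40, p).

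The trial has a single arm and its main result is one rate compared with a fixed 25%, so a shift in that rate has no control arm to offset it. The rule also gives an effective drug a chance of being stopped early, which the power statement leaves out. Because 3.3 fixes no threshold and other sections omit the condition, a reader of the final report could not tell how much selection took place.

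**Working it through.** **Inputs.** N = 40, assumed rate 50% and reference rate 25% (Protocol 10.3, SAP 1.4 and 5.1); 6 to 9 subjects per Phase 1b dose level (Protocol 5.2.1); about 34 in Phase 2 (synopsis, SAP 1.2), so 6 + 34 = 40. The efficacy threshold is not in the documents. I assume a rule of at least g responders among 6 and show g = 1, 2 and 3.

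**Step 1: the plan's own power figure.** The Clopper-Pearson lower 95% bound is 0.2704 for 17/40 and 0.2486 for 16/40, so success needs at least 17. The protocol's > and the SAP's ≥ give the same cut-off.
- P(Bin(40, 0.50) ≥ 17) = 86.6%
- P(Bin(40, 0.25) ≥ 17) = 1.16%

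The stated 90% is therefore not reproduced, with no efficacy condition involved. A Wilson (score) interval has cut-off 16 and gives 92.3%; the exact interval at N = 42 gives 91.8%.

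**Step 2: adding the continuation rule.** Let K be the number of responders among the 6.
- Chance of success over all trials = Σ over k ≥ g of P(K = k) × P(Bin(34, p) ≥ 17 − k)
- Chance of success given that Phase 2 opens = the line above ÷ P(K ≥ g)
- Bias given that Phase 2 opens = (E[K | K ≥ g] − 6p) ÷ 40

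Example, g = 2 and p = 0.50. The rule loses the paths with K = 0 and K = 1: 0.8659 − (0.0156 × 0.5679 + 0.0938 × 0.6962) = 0.792. For the bias, P(K ≥ 2) = 57/64 = 0.8906 and E[K | K ≥ 2] = (3 − 6/64) ÷ 0.8906 = 3.263, so bias = 0.263 ÷ 40 = 0.7 points.

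| Assumed rule | Power at 50%, all trials | Power at 50%, given Phase 2 opens | Bias at 50%, given Phase 2 opens | Bias at 25%, given Phase 2 opens | Rejection at 25%, all trials | Rejection at 25%, given Phase 2 opens |
|---|---|---|---|---|---|---|
| none | 86.6% | 86.6% | 0 | 0 | 1.16% | 1.16% |
| ≥1 of 6 | 85.7% | 87.1% | +0.1 | +0.8 | 1.13% | 1.37% |
| ≥2 of 6 | 79.2% | 88.9% | +0.7 | +2.4 | 0.98% | 2.09% |
| ≥3 of 6 | 60.3% | 91.9% | +1.8 | +4.4 | 0.63% | 3.71% |

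Bias is in percentage points.

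**Step 3: nine Phase 1b subjects and 31 in Phase 2.** Rules of at least 2, 3 or 4 of 9 give power over all trials of 85.6%, 81.1% or 68.6%. The bias given that Phase 2 opens is 0.2, 0.7 or 1.6 points at 50%, and 1.6, 3.3 or 5.3 points at 25%.

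**Step 4: early reading.** The first scheduled response assessment after baseline is Week 5 (Protocol 7.2.1), at the end of the 28-day DLT window. Suppose, as an assumption, that an eventual responder has responded by then with probability 0.7 or 0.5. A rule of at least 2 of 6 at Week 5 then gives power over all trials of 61.5% or 42.5%. The bias is 1.2 or 1.6 points at 50%, and 2.8 or 3.1 points at 25%.

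**Step 5: Phase 2 subjects alone.** With n = 34 the lower bound is 0.2719 for 15/34 and 0.2465 for 14/34, so the cut-off is 15. Power at 50% is 80.4% and rejection at 25% is 1.17%.

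**The case against.** The strongest reply is that the primary test remains valid. A rule that can only stop the trial cannot create false positives, and over all trials the rejection rate at 25% falls from 1.16% to 0.98% or 0.63% under rules of 2 or 3 of 6. That stands. A reader might infer an inflated type I error; the documents do not support it. Rejection given that Phase 2 opens does rise, but among the six-subject rules shown it passes 2.5% only at 3 of 6.

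The upward bias is also conditional. If stopped trials are counted with their Phase 1b rate as the estimate, the mean at a true 50% is 0.493, 0.467 or 0.434, which is below the truth. Power and bias must be read in their own frames: given that Phase 2 opens, power at 50% goes up. Both points stand.

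At the design rate the bias is under 2 points for the six-subject rules in the table, because only 6 of 40 subjects are selected. A demanding rule such as 4 of 6 would give larger figures, but nothing in the documents points to one.

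It can be said that an early reading dilutes the selection. That is true if favourable meant something loosely tied to response, such as absence of progression. It is not true for a fixed count of early responders: a Week 5 response already counts as a best overall response, and Step 4 shows larger effects.

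Finally, Protocol 5.2.3 gives a sequence and does not exclude further conditions, and the dose-level review in 5.2.1 concerns dose selection. The sections are therefore incompletely aligned rather than flatly opposed, apart from the synopsis entry on interim analysis.

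**Conclusion.** The point holds in a limited form. Protocol 3.3 introduces an efficacy decision that is undefined and absent from the other descriptions of the transition. The subjects it looks at are reused in an unadjusted primary analysis. Given that Phase 2 opens, the pooled rate overstates the true rate by about 0.1 to 1.8 points at 50% and 0.8 to 4.4 points at 25%, for rules of 1 to 3 of 6 applied to final best response. The real size cannot be fixed from the documents because no threshold is given.

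The larger consequence is for power. The planned exact interval gives 86.6% with no efficacy condition, and 85.7%, 79.2% or 60.3% over all trials with those rules. The 3.4-point shortfall from 90% to 86.6% is separate and should not be attributed to 3.3.

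Nor do the documents support the conclusion that efficacy must be taken out of 3.3. That would drop a stated check before about 34 more subjects are exposed, and Protocol 12.16 would still let the sponsor stop at any time.

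**What to change.** 1. In SAP 5.1, add the response rate and exact 95% interval in subjects enrolled in Phase 2 only (about 34), reported beside the pooled primary result as the estimate unaffected by the Phase 1b decision. Cost: one table and a wider interval. Its power at 50% is 80.4% with cut-off 15/34, so it should support the pooled analysis and not replace it.

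2. In Protocol 10.3 and SAP 1.4, restate the power as about 87% for the exact interval at N = 40 before any efficacy decision, and say that the decision in 3.3 lowers it further. Cost: a sentence in each document, and a figure below 90%.

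3. Reconcile Protocol 3.3 with the synopsis, Protocol 3.1 and 5.2.3 and SAP 1.2 on whether efficacy is part of the decision to open Phase 2. If it is, state the measure, time point and cut-off so that the power can be calculated with it. Cost: a text edit, and some loss of sponsor flexibility if a cut-off is written down.

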3.3.1. Phase 1b DLT Schema

4. SUBJECT SELECTION

4.1. Inclusion Criteria

To be enrolled in the study, each potential subject must satisfy all of the following inclusion criteria.

1. Steroid dependent/refractory classic cGVHD defined at any time post-HCT as:
 - a) Dependent disease – Persistent cGVHD manifestations requiring a glucocorticoid dose \geq prednisone 0.25 mg/kg/day (0.5 mg/kg orally every other day or equivalent) for at least 12 weeks.

- b) Refractory disease - Progressive cGVHD manifestations despite treatment with a glucocorticoid dose \geq prednisone 0.5 mg/kg/day (1 mg/kg orally every other day or equivalent) for at least 4 weeks.
2. No more than 3 previous treatments for cGVHD. Treatment with glucocorticoids is considered a treatment for cGVHD and should be included in determining the number of previous treatments. Participants may have received ibrutinib pre-transplant for other reasons besides cGVHD such as for the treatment of leukemia or lymphoma.
3. Participants must be receiving baseline systemic glucocorticoid therapy for cGVHD at study entry. The dose of steroids must be stable for 28 days prior to starting ibrutinib
4. At the time of trial enrollment, participants may be receiving other immunosuppressive therapies in addition to glucocorticoids. Immunosuppressant doses must be stable for 28 days prior to starting ibrutinib. Monoclonal T and B cell antibodies must be discontinued at least 56 days before starting ibrutinib.
5. Chronic GVHD manifestations ([Appendix B](#)) that can be followed on physical or laboratory exam including at least one of the following criteria:
 - $>25\%$ BSA NIH-defined criteria “Erythematous rash”
 - >4 total mouth score by NIH-defined criteria
6. Clinically stable or worsening cGVHD between Screening and Day 1 cGVHD response assessment (see [Section 7.1.3](#) for details).
7. ≥ 18 years of age
8. Life expectancy ≥ 6 months
9. Karnofsky performance status ≥ 60 (see [Appendix C](#)).
10. Adequate hepatic and renal function as defined as:
 - a) Serum creatinine ≤ 1.5 x ULN
 - b) Aspartate aminotransferase (AST), alanine aminotransferase (ALT) and alkaline phosphatase ≤ 3 x ULN or of non-hepatic origin, such as hemolysis
 - c) Total bilirubin ≤ 2 x ULN (unless bilirubin rise is due to Gilbert’s syndrome or of non-hepatic origin)
 - d) Estimated Creatinine Clearance ≥ 30 mL/min (using Cockcroft-Gault formula)
11. Adequate hematological function defined as:
 - a) Absolute neutrophil count (ANC) $\geq 1.0 \times 10^9$ /L and off growth factor support x 7 days
 - b) Platelets $\geq 30 \times 10^9$ /L and no transfusion support x 7 days
 - c) Hemoglobin ≥ 8 g/dL and no transfusion or growth support x 7 days
12. PT/INR < 1.5 x ULN and PTT (aPTT) < 1.5 x ULN (unless abnormalities are unrelated to coagulopathy or bleeding disorder).
13. ≤ 6 stools per day

14. Oxygen saturation after exertion maintained at $\geq 88\%$ on room air. If not, forced expiratory volume in 1 second (FEV1) $\geq 50\%$ on pulmonary function tests performed within 6 months of study entry.
15. Ability to understand and willingness to sign a written informed consent form (ICF).
16. Myeloablative or non-myeloablative allogeneic hematopoietic cell transplant for underlying hematological disease.
17. Female subjects who are of non-reproductive potential (ie, post-menopausal by history - no menses for ≥ 1 year; OR history of hysterectomy; OR history of bilateral tubal ligation; OR history of bilateral oophorectomy). Female subjects of reproductive potential must have a negative serum pregnancy test upon study entry.
18. Male and female subjects of reproductive potential who agree to use highly effective methods of birth control (eg, condoms, implants, injectables, combined oral contraceptives, some intrauterine devices [IUDs], complete abstinence¹, or sterilized partner) during the period of therapy and for 90 days after the last dose of ibrutinib.

4.2. Exclusion Criteria

To be enrolled in the study, potential subjects must meet NONE of the following exclusion criteria:

1. Known or suspected active acute GVHD
2. Received any investigational agents ≤ 28 days before starting ibrutinib.
3. Current treatment with sirolimus AND either cyclosporine or tacrolimus.
4. History of treatment with a tyrosine kinase inhibitor (eg imatinib) purine analogs, or other cancer chemotherapy in the 4 weeks prior to starting ibrutinib.
5. Currently active, clinically significant cardiovascular disease, such as uncontrolled arrhythmia or Class 3 or 4 congestive heart failure as defined by the New York Heart Association Functional Classification; or a history of myocardial infarction, unstable angina, or acute coronary syndrome within 6 months prior to randomization.
6. Any uncontrolled active systemic infection or infection requiring systemic treatment that was completed ≤ 7 days before the first dose of ibrutinib.
7. Progressive underlying malignant disease including post-transplant lymphoproliferative disease.
8. History of other malignancy (not including the underlying malignancy that was the indication for transplant), with the following exceptions:

¹ Complete abstinence is a highly effective method only if defined as refraining from heterosexual intercourse during the entire period of risk associated with the study treatments. The reliability of sexual abstinence needs to be evaluated in relation to the duration of the clinical trial and the preferred and usual lifestyle of the subject.
http://www.hma.eu/fileadmin/dateien/Human_Medicines/01_About_HMA/Working_Groups/CTFG/2014_09_HMA_CTFG_Contraception.pdf

- Malignancy treated with curative intent and with no evidence of active disease present for more than 3 years prior to screening and felt to be at low risk for recurrence by treating physician;
 - Adequately treated nonmelanomatous skin cancer or lentigo maligna melanoma without current evidence of disease;
 - Adequately treated cervical carcinoma in situ without current evidence of disease.
9. Subject is pregnant, breast-feeding, or of childbearing potential without a negative serum or urine pregnancy test within 7 days of enrollment. Male or female patients of childbearing potential unwilling to use effective contraceptive precautions throughout the trial.
 10. Subject not willing to comply with treatment or response evaluation.
 11. Moderate or severe hepatic impairment (Child-Pugh classification, see [Appendix K](#)).
 12. Subject has a concurrent illness which in the opinion of the investigator may interfere with the treatment and evaluation of the patient.
 13. Concomitant use of warfarin or other Vitamin K antagonists
 14. Subject has a known allergy or hypersensitivity to ibrutinib.
 15. Vaccinated with live, attenuated vaccines within 4 weeks of first dose of ibrutinib.
 16. Known bleeding disorders (eg, von Willebrand's disease or hemophilia).
 17. History of stroke or intracranial hemorrhage within 6 months prior to enrollment.
 18. Known history of human immunodeficiency virus (HIV) or active with hepatitis C virus (HCV) or hepatitis B virus (HBV). Subjects who are positive for hepatitis B core antibody, hepatitis B surface antigen, or hepatitis C antibody must have a negative polymerase chain reaction (PCR) result before enrollment. Those who are PCR positive will be excluded.
 19. Major surgery within 4 weeks of first dose of ibrutinib.
 20. Concurrent use of a strong cytochrome P450 (CYP) 3A inhibitor ([Appendix I](#)).
 21. Unable to swallow capsules or malabsorption syndrome, disease significantly affecting gastrointestinal function, or resection of the stomach or small bowel, symptomatic inflammatory bowel disease or ulcerative colitis, or partial or complete bowel obstruction.
 22. Unable to understand the purpose and risks of the study and to provide a signed and dated informed consent form (ICF) and authorization to use protected health information (in accordance with national and local subject privacy regulations).

5. TREATMENT OF SUBJECTS

5.1. Treatment Allocation and Blinding

This is an open label study and no randomization will occur.

5.2. Study Treatment

5.2.1. Phase 1b Dose Selection and Stopping Rules

Three dose levels of ibrutinib may be tested: 140 mg/day, 280 mg/day and 420 mg/day. The starting dose will be 420 mg/day and the dose will be modified based on the dose limiting toxicities (DLTs).

Phase 1b will follow a modified 3+3+3 design with 6-9 subjects at each dose level. The dose will be selected as the RP2D if the subject incidence of DLTs during the first 28 days of study treatment is <33%. Before determining the RP2D, 6 subjects in any given cohort must have completed the DLT observation period which is defined as 28 days of therapy. Using the modified 3+3+3 design, the maximum tolerated dose (MTD) is exceeded when ≥ 3 out of 9 subjects in a dose level experience a DLT. If there are 3 DLTs at a dose level, the MTD is exceeded and then the next lower dose level will be enrolled.

Enrollment in a dose level will proceed as follows:

- If no DLT is observed during the DLT observation period in the initial 3 subjects of a dose level, then a second group of 3 subjects will be enrolled at the same dose level for a total of 6 subjects. If 0-1 DLT occur out of 6 subjects, then this dose will be the RP2D. If 2 DLTs occur out of 6, then the dose level cohort will be expanded to enroll a total of 9 subjects. If no further DLTs occur then this dose will be the RP2D.
- If 1 DLT is observed in the initial 3 subjects, the dose level will be expanded to enroll 3 additional subjects at the same dose level for a total of at least 6 subjects. If no further DLT(s) are observed, then this dose will be the RP2D. If 2 DLTs are observed out of 6 subjects, then the dose level will be expanded to enroll a total of 9 subjects. If no further DLTs are observed in this group of subjects then this dose will be the RP2D.
- If 2 DLTs are observed in the initial 3 subjects, then enrollment to this dose level will be stopped. A DLT review will occur to determine if the dose should be lowered.
- If 3 DLTs are observed, then the dose level will be stopped and the next lower dose will be assessed.

If a subject experiences a DLT during the DLT observation window, the subject will discontinue treatment.

The decision to proceed with a RP2D or to dose reduce will be made in a Dose Level Review Meeting by the Sponsor in conjunction with the investigators after careful consideration of all available safety and laboratory information.

